### **7.5.8. Intra-articular Injection Procedure**

IA injections will be performed by the assigned injector. The injector may choose the position of the knee (e.g., extended or flexed), the approach for the injection (e.g., medial or lateral) and the numbing agent to be used (e.g., ethyl chloride, subcutaneous lidocaine; IA anesthetics are not allowed) based on standard of care. Sterile technique should be used.

Prior to injection, the index knee should be thoroughly cleansed using a bactericidal solution. The index knee will be aspirated in all cases prior to administration of study medication.

Following attempted aspiration, 5 mL of the reconstituted FX006 will be injected into the synovial space. Refer to the Pharmacy Binder for detailed instructions on how to prepare FX006.

The same needle used for IA injection of the study medication may also be used for synovial fluid aspiration, thereby allowing for a single injection with syringe replacement. The injector will use a 21 gauge or larger needle for injection and aspiration of fluid.

Patients should be advised to avoid strenuous activities or prolonged weight-bearing activities for approximately 24 to 48 hours following the injection and to also maintain a stable lifestyle with regard to physical activity throughout the duration of the study.

In the event that the patient has an immediate reaction (e.g., tenderness, increased pain, swelling, effusion, decreased mobility of the index knee), the patient should be treated according to local clinical guidelines and physician experience (see also Protocol Section Section 8.1.5).

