**Table 1: Schedule of Study Assessments**

Procedures	Screen 	Baseline Day 1	Week 4 	Week 8 	Week 12, 16, 20, 24 	Week 28, 32, 36, 40, 44, 48 	Week 52  /End of Study
Informed consent	X 						
Inclusion/Exclusion Review	X	X 					
Medical History/Update	X	X 					
OA Medical History	X						
Prior Treatment & Medications	X 	X 					
Physical Examination	X				X 		X
Index Knee X-ray 	X						X 
Index Knee Assessment 	X	X 			X 		X
12-Lead ECG	X						
Vital Signs	X	X 			X 		X
Height	X						
Weight and BMI	X						X
Hematology & Chemistry 	X				X 		X
HIV, Hepatitis B/C 	X						
Serum Pregnancy Test 	X						
Urine Pregnancy Test 		X 			X 		X
WOMAC 	X	X 	X	X	X	X	X
KOOS QOL 		X 	X	X	X	X	X
GPAQ 		X 			X 		
Measured Function Device 			X				
Index knee aspiration and collection of synovial fluid		X 			X 		
1 st treatment administration		X					
Evaluation for repeat administration					X		
2 nd (repeat) treatment administration					X 		
AEs & ConMeds 					X		

 Screening period is a minimum of 7 days, up to 21 days.

 Visit should be conducted within +/- 7 days from scheduled date.

 Consent must be obtained prior to any study-specific procedures.

 Complete assessment prior to dosing.

 Record any prior medications received within 30 days prior to the Screening visit.

 To be completed prior to dosing only if patient is to receive the 2nd dose of FX006. For patients not eligible to receive 2nd dose, complete at the final study visit.

 Standing, fixed flexion PA view, weight bearing X-ray of the index knee will be taken using a standardized knee positioning device. The Screening X-ray will be read locally for K-L grade. The Screening and Week 52 X-rays will be sent to central imaging vendor for safety assessment.

 End of Study x-ray will only be performed if patient has received a repeat administration of FX006.

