 Index knee will be assessed for tenderness, heat/redness, swelling, effusion, and Baker's cyst. New clinically significant findings or findings that worsen for the patient's baseline condition should be recorded as AEs.

 Via Central Laboratory.

 Conduct for women of childbearing potential only.

 Patient questionnaires to be completed prior to all other assessments.

 Complete GPAQ at Week 12 only regardless of when and if second dose is given.

 Steps per day will be captured using a measured function device. Patients will be provided with a device at the Screening visit to be worn for at least 7 days prior to Baseline/Day 1 through Week 12. The site will confirm patient compliance with wearing the device to capture steps per day data at each patient visit from Day 1 through Week 12.

 To be completed prior to dosing only if patient is to receive the 2nd dose of FX006.

 Repeat administration may occur at either Week 12, 16, 20, or 24.

 AEs and Concomitant Medications will be captured from Day 1 (post injection) to Week 12 or 24 for patients who only receive a single injection or to Week 52 for patients who receive a second injection or to Early Discontinuation Visit for patients who discontinue the study early.

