#### 4.2.9. Visit Windows

All data listings that contain an evaluation date will contain a relative study day (Rel Day Dose 1). Pre-treatment and post-treatment study days are numbered relative to the day of the first dose of study treatment, which is designated as Day 1. The preceding day is Day -1, the day before that is Day -2, etc. Listings will also contain a study day (Rel Day Dose 2) relative to the second dose of study treatment, which is designated as Day 1. For patients that do not receive a second dose, Rel Day Dose 2 will be "NA". For Rel Day Dose 2, preceding days (e.g., Day -1, -2) will not be derived or presented. In other words, if the date is prior to Dose 2, only Rel Day Dose 1 will be presented. If the date is after Dose 2, then both Rel Day Dose 1 and Rel Day Dose 2 will be presented.

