##### Steps per Day (Fitbit) data windowing:

The visit windows to be used for computing steps per day are provided in [Table 2](#). Observations collected in these windows will be averaged and presented according to the nominal visit label for that window.

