**Table 2      Evaluation Intervals for the Data Points to be Included in the Table**

Visit	Relative Day Interval for Analysis
Baseline	Day -7 to Day -1
Week 1	Day 1 to Day 7
Week 2	Day 8 to Day 14
Week 3	Day 15 to Day 21
Week 4	Day 22 to Day 28
Week 5	Day 29 to Day 35
Week 6	Day 36 to Day 42
Week 7	Day 43 to Day 49
Week 8	Day 50 to Day 56
Week 9	Day 57 to Day 63
Week 10	Day 64 to Day 70
Week 11	Day 71 to Day 77
Week 12	Day 78 to Day 84

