#### **4.9.3. Daily activity measured as steps per day**

Steps per day data are collected from baseline to Week 12, so analysis only applies to a single injection of FX006. Weekly mean steps per day from Fitbit data will be calculated for baseline through Week 12 using the visit windows presented in section 4.2.9. Values of <1000 will be set to missing since they were considered invalid upon review of the data. Handling of missing data is presented in section 4.2.8.

A cumulative activity score will be calculated for each patient, defined as the incremental sum of the weekly average between Weeks 1 and 12. Incremental sum of weekly mean steps per day will be calculated as follows:

- Incremental sum (Week 1) = Weekly mean steps per day (Week 1)
- Incremental sum (Week 2) = Incremental sum (Week 1) + Weekly mean steps per day (Week 2)
- Incremental sum (Week x) = Incremental sum (x-1) + Weekly mean steps per day (Week x)

Descriptive statistics will include number of observations, unadjusted mean, standard deviation, median, minimum and maximum values by week. Values presented will be actual weekly mean steps per day, change from baseline in weekly mean steps per day, and incremental sum of weekly mean steps per day. A line plot will present each of these values by week.

A responder analysis will be performed in the same way that is described in section 4.9.1.3. Steps per day (Fitbit) responders are defined as patients who have  $\geq 10\%$  increase in weekly mean steps per day from baseline at a given visit.

The correlation between change from baseline in steps per day and change from baseline in WOMAC A, B, C and total score and the KOOS QOL subscale at Week 4, Week 8 and Week 12 will be explored. Pearson correlation will be used if both parameters are normally distributed. Spearman correlation will be used if either parameter is not normally distributed. The mean and median values for each parameter and the correlation coefficient will be presented in a table. Change from baseline for WOMAC A, B, C and total score and the KOOS QOL subscale versus change from baseline for average steps per day at Week 4, Week 8 and Week 12 will be presented in scatter plots, which will also include a best fit line.

A data listing will present steps per day for each patient as well as number of days that contributed to each weekly average and the number that were missing.

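### The SAP's Week 12 step window is not cut at the second dose, so the single-injection statement is not guaranteed; separately, Week 1 contains the advised low-activity days.

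*SAP*

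**What the plan says.** SAP 4.9.3 claims: "Steps per day data are collected from baseline to Week 12, so analysis only applies to a single injection of FX006".

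The windows are in SAP 4.2.9. Days are counted "relative to the day of the first dose of study treatment, which is designated as Day 1". Table 2 runs from a baseline week (Day -7 to -1) through Week 1 (Day 1 to 7) to Week 12, "Day 78 to Day 84". The averaging rule is: "Observations collected in these windows will be averaged and presented according to the nominal visit label for that window". SAP 4.2.8 requires three valid days out of seven, and SAP 4.9.3 treats values below 1000 as missing. Neither section mentions the date of the second dose.

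The footnotes to Protocol Table 1 say "Visit should be conducted within +/- 7 days from scheduled date" and "Repeat administration may occur at either Week 12, 16, 20, or 24". Protocol 7.9.11 has the device worn through Week 12 but does not say whether wear stops at the visit or on a calendar day. Protocol 7.5.8 adds: "Patients should be advised to avoid strenuous activities or prolonged weight-bearing activities for approximately 24 to 48 hours following the injection".

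For WOMAC, the SAP does have a cut. The first-dose group in 4.9.1.1 and 4.9.1.3 ends at the second dose if that comes first.

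**The concern.** A fixed calendar window that ends at about the time of a visit with a two-sided tolerance can run past that visit. If the second injection is given at that visit, days from the second-dose period are averaged into a result labelled as single-injection. The outputs exposed are the Week 12 mean, change from baseline, 10% responder rate and correlations and, slightly, the cumulative score. The questionnaires are completed before other assessments at the visit, so a Week 12 correlation could pair a pre-dose WOMAC or KOOS score with steps that are partly post-dose.

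Week 1 raises a different issue. It compares a week that starts with an injection and advice to limit activity against a baseline week without either. A lower Week 1 mean could reflect the advice rather than any effect of the drug.

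**Working it through.** **Table 2 reproduced.** Week w covers Day 7(w-1)+1 to Day 7w. This gives Week 1 = Day 1-7, Week 4 = Day 22-28, Week 8 = Day 50-56 and Week 12 = Day 78-84, matching the SAP.

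**Week 12 overlap.** The documents do not say which study day is nominal Week 12. Counting 84 days after Day 1 gives Day 85, with a permitted range of Day 78 to 92. For re-dosing on Day d, with d from 78 to 85:

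- window days on or after dosing = 85 - d
- window days strictly after dosing = 84 - d (0 at d = 85)
- window days before dosing = d - 78

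| Visit day | Days early | On or after dosing | Strictly after | Before dosing |
|---|---|---|---|---|
| 78 | 7 | 7 | 6 | 0 |
| 79 | 6 | 6 | 5 | 1 |
| 80 | 5 | 5 | 4 | 2 |
| 81 | 4 | 4 | 3 | 3 |
| 82 | 3 | 3 | 2 | 4 |
| 83 | 2 | 2 | 1 | 5 |
| 84 | 1 | 1 | 0 | 6 |
| 85 or later | 0 | 0 | 0 | 7 |

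If nominal Week 12 is Day 84 instead, an on-time visit puts the dosing day in the window. A visit seven days early (Day 77) then puts all seven window days strictly after dosing, with the dosing day itself in Week 11. Weeks 2 to 10 are untouched on either count.

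**Size of a Week 12 effect.** If m of 7 days differ by a fraction e, the weekly mean shifts by m x e / 7. The documents give no value for e. Taking e from -30% to +10% as an assumption:

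- m = 1: -4.3% to +1.4%
- m = 6: -25.7% to +8.6%

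On the 12-week sum, with otherwise equal weeks, the shift is m x e / 84. For m = 6 that is -2.1% to +0.7%.

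**Week 1.** The 24 to 48 hours after a Day 1 injection fall on Days 1-2 or Days 1-3, so 2/7 = 29% or 3/7 = 43% of the window. If steps fall by a fraction r on k such days, the Week 1 mean falls by k x r / 7 and the 12-week sum by k x r / 84. Taking r from 10% to 50% (an assumption, not in the documents):

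- k = 2: Week 1 falls by 2.9% to 14.3%, the sum by 0.2% to 1.2%
- k = 3: Week 1 falls by 4.3% to 21.4%, the sum by 0.4% to 1.8%

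**Correlation timing.** On the same count, the Week 4 visit may fall on Day 22 to 36 (Day 29 +/- 7), against a fixed window of Day 22-28. For an on-time visit the window is exactly the seven days before it. At the extremes the window starts on the visit day or ends eight days before it. Week 8 behaves the same way.

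**The case against.** The strongest reply is that wearing the device through Week 12 most naturally means until about that visit. Then at most the dosing day enters the window and the SAP sentence is essentially true. That limits the size of the problem but does not close it: the protocol does not say when wear ends, and the windowing rule would average any later days that exist.

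A second reply is that steps are an exploratory, mainly descriptive endpoint in a single-arm safety study, that the listing shows how many days fed each weekly mean, and that SAP 4.9.5 permits sensitivity analyses. This bears on severity. A listing does not correct the summary tables, and 4.9.5 would label any later check post-hoc.

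Several stronger readings are tempting but not supported:

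- A reader might infer that the Week 1 rest days contradict the single-injection statement. They follow the first injection, so they do not. The advice concerns strenuous or prolonged weight-bearing activity, not ordinary walking, so the size of any fall in steps is unknown. The rule on values below 1000 may remove some very low days, but only selectively. A Week 1 responder rate may not even be planned, since 4.9.1.3, which the step analysis follows, starts at Week 4.
- A reader might spread visits evenly over Day 78-92 and conclude that 7/15 = 47% of patients are affected. No document supports even spacing, and the figure counts all Week 12 visits, not only those with re-dosing. SAP section 5 says more than 90% received a second dose, but that covers all eligible visits together.
- A reader might treat contamination and data loss at Week 12 as adding up. For one patient they exclude each other: contamination beyond the dosing day needs continued wear, and loss needs wear to stop at the visit.
- A reader might call Week 12 the main step time point. Neither document says so.

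**Conclusion.** The concern holds in a limited form. As written, the windowing rule does not secure the single-injection statement in SAP 4.9.3. For patients re-dosed at an early Week 12 visit, 1 to 7 of the 7 window days lie on or after the second-dose date (Day 85 count). More than the dosing day contributes only if the device is still worn. On-time and late visits are unaffected on that count, and the number of patients involved cannot be worked out from the documents.

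The Week 1 issue is separate. Every patient has 2 to 3 advised low-activity days in that window and none in the baseline week. The effect on the Week 1 mean is unknown; under the assumed 10% to 50% fall it is 2.9% to 21.4%, with at most 1.8% on the cumulative score.

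The step results as a whole are not invalidated. The Week 4 and Week 8 correlations cannot contain second-dose days at scheduled re-dosing; their only weakness is imperfect alignment with the visit. This is a minor point on an exploratory endpoint, worth fixing because the remedy is cheap and the SAP already uses the same cut for WOMAC.

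**What to change.** In SAP 4.2.9 and 4.9.3:

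1. Exclude step values dated on or after the second dose from every weekly window, matching the WOMAC first-dose group, and keep the three-of-seven rule.
2. Keep Table 2 for the weekly summaries and the cumulative score. Moving the Week 4, 8 and 12 windows to the visit date there would make them overlap neighbouring weeks: a Day 36 visit would turn Week 4 into Day 29-35, which is already Week 5.
3. For the step correlations only, use the seven days before the actual visit and before any second dose.
4. Add a supplementary Week 1 row without Days 1-3. Four days remain, so the three-day minimum can still be met.
5. State which study day is nominal Week 12 and when device wear ends.

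The cost is SAP wording and light programming, with no new data. On the Day 85 count, Week 12 becomes missing for patients re-dosed 5 to 7 days early, who keep only 2, 1 or 0 days. Their Week 12 cumulative score then cannot be computed from the formula as written, so the SAP should say how that is handled. The correlation window recovers pre-visit days for these patients; for late visits it needs wear to continue up to the visit. No change to the dosing schedule or the activity advice is implied.

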#### 4.9.4. GPAQ

GPAQ domains (activity at work, travel to and from places and recreational activities) and total will be presented descriptively at the two time points collected (baseline and Week 12). Average MET-minutes of moderate or vigorous physical activity per day will be calculated by domain and overall according to the GPAQ Analysis Guide. The change in average MET-minutes of physical activity per day from baseline to Week 12 will also be presented.

Missing data rules are presented in section 4.2.8. Descriptive statistics will include number of observations, unadjusted mean, standard deviation, median, minimum and maximum. These statistics will be presented for all patients combined.

The correlation between change from baseline in average MET-minutes per day from the total GPAQ (all domains combined) and change from baseline in average steps per day will be explored at baseline and Week 12 separately for all patients combined. Pearson correlation will be used if both parameters are normally distributed. Spearman correlation will be used if either parameter is not normally distributed. The mean and median values by visit for each parameter, and the correlation coefficient by visit will be presented in a table. Average MET-minutes per day versus average steps per day for each visit will be presented in scatter plots, which will also include a best fit line.

#### 4.9.5. Sensitivity Analyses

Sensitivity analyses may be performed if required to better understand study results. Any sensitivity analyses will be identified as post-hoc in the clinical study report.

### 4.10. Safety Analyses

Safety analyses will be conducted using the SP. All change from baseline values will be calculated based on the pre-dose (screening) value.

#### 4.10.1. Adverse Events

Adverse events will be coded using the MedDRA (version 19.1) coding system and displayed in tables and data listings using system organ class (SOC) and preferred term (PT).

Analyses of AEs will be performed for those events that are considered treatment-emergent, where treatment-emergent is defined as any AE with onset after the administration of study treatment, or any event that was present at baseline but worsened in intensity through the end of the study.

If the start date/time of an AE is partially or completely missing, the date/time will be compared as far as possible with the date/time of the start of administration of study drug. The AE will be assumed to be treatment emergent if it cannot be definitively shown that the AE did not occur or worsen during the treatment-emergent period (worst case approach). The following general rules will be used:

- If the start time of an AE is missing but the start date is complete, an AE will only be excluded as being treatment emergent if the start date is before the date of study drug administration or if the stop date/time is before study drug administration.
- If the start time and day are missing but the start month and year are complete, an AE will only be excluded as being treatment emergent if the start month/year is before the month/year of study drug administration or if the stop date/time is before study drug administration.
- If the start day and month are missing but the start year is complete, an AE will only be excluded as being treatment emergent if start year is before the year of study drug administration or if the stop date/time is before study drug administration.
- If the start date is completely missing, an AE will be considered treatment-emergent unless the stop date/time is before study drug administration.

Adverse events will be summarized by patient incidence rates; therefore, in any tabulation, a patient contributes only once to the count for a given SOC or preferred term.

Summary tables will display the number and percentage of patients who experienced at least one TEAE in each of the following categories:

- Any TEAE
- Any Serious Adverse Event (SAE)
- Any TEAE leading to study discontinuation
- Any TEAE by severity (grade 1-5)
- Any TEAE by relationship
- Any index-knee related TEAE
- Any index-knee related SAE
- Any index-knee related TEAE leading to study discontinuation

- Any index-knee related TEAE by severity (grade 1-5)
- Any index-knee related TEAE by relationship
- Any TEAE related to injection procedure

Separate tabulations will be produced for each of following categories:

- All TEAEs by SOC and PT
- All SAEs by SOC and PT
- All TEAEs related to study drug by SOC and PT
- All TEAEs related to injection procedure by SOC and PT
- All TEAEs by maximum severity by SOC and PT
- All TEAEs leading to study discontinuation
- All TEAEs leading to death
- All index-knee related TEAEs by SOC and PT
- All index-knee related TEAEs related to study drug by SOC and PT
- All index-knee related TEAEs by maximum severity by SOC and PT

Summary tables and the tabulation of All TEAEs by SOC and PT will be presented for the following patient groups and time periods, with a separate table for each patient group:

1. Patients receiving only one dose
  - a. First dose to Week 12
  - b. First dose to Week 24 (end of study)
2. Patients receiving the second dose at Week 12
  - a. First dose to Week 12
  - b. Week 12 to Week 24
  - c. Week 12 to Week 52
3. Patients receiving the second dose at Week 16
  - a. First dose to Week 16
  - b. Week 16 to Week 32
  - c. Week 16 to Week 52
4. Patients receiving the second dose at Week 20
  - a. First dose to Week 20
  - b. Week 20 to Week 40
  - c. Week 20 to Week 52
5. Patients receiving the second dose at Week 24
  - a. First dose to Week 24
  - b. Week 24 to Week 48
  - c. Week 24 to Week 52

Summary tables and all tabulations will be presented for the following time periods for patients receiving two doses only (same table):

1. Baseline to Week 52
2. Baseline to Week 12
3. Second dose to 12 weeks after second dose

Date and time of onset of TEAE will be used to assign the time periods.

In the summary table for "Any TEAE by SOC and PT", an additional row with the number of events observed will be presented. A patient will be counted once for the number of patients if they have multiple events. The total number of events will be the absolute number of events observed, and a patient will be counted more than once for the event totals if they have multiple events.

In these tabulations, related is defined as any TEAE deemed possibly, probably or definitely related to study drug by the investigator. If relationship is missing, it will be imputed as related.

If an event has a TEAE start date that, after imputation rules are applied, is not complete enough to determine the time period in which the TEAE occurred, that event will not be included in the tabulations by study day.

Formal hypothesis-testing of AE incidence rates will not be performed.

By-patient listings will be provided for the following, for all patients: patient deaths, SAEs and AEs leading to discontinuation.

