### **8.1.2. Evaluating and Recording of Adverse Events**

At each visit all AEs that occur from the time of treatment and throughout a patient’s study participation that are observed, elicited by the site personnel, or reported by the patient, will be recorded in the source documentation and appropriate section of the AE eCRF and evaluated by an assessor.

Minimum information required for each AE includes type of event, duration (start and end dates), severity, seriousness, causality to investigational medicinal product, action taken, and outcome.

Severity of AEs will be graded by the Principal Investigator using the Common Terminology Criteria for AEs (CTCAE) version 4.0 (refer to the Study Manual or [http://ctep.cancer.gov/protocolDevelopment/electronic\\_applications/ctc.htm](http://ctep.cancer.gov/protocolDevelopment/electronic_applications/ctc.htm)).

For AEs not listed in the CTCAE, the following definitions should be used:

Grade 1	Mild Symptomatic or mild symptoms Clinical or diagnostic observations only Intervention not indicated
Grade 2	Moderate Minimal, local or noninvasive intervention indicated Limiting age-appropriate instrumental activities of daily living (ADL)*
Grade 3	Severe or medically significant but not immediately life-threatening Hospitalization or prolongation of hospitalization indicated Disabling Limiting self care ADL**
Grade 4	Life-threatening consequences Urgent intervention indicated
Grade 5	Death related to AE

\*Instrumental ADL refer to preparing meals, shopping for groceries or clothes, using the telephone, managing money, etc.

\*\*Self care ADL refer to bathing, dressing and undressing, feeding self, using the toilet, taking medications, and not bedridden.

The relationship of the AE to the investigational medicinal product should be specified by the Principal Investigator, using the following definitions:

1. Not Related: Concomitant illness, accident or event with no reasonable association with treatment.
2. Unlikely: The reaction has little or no temporal sequence from administration of the investigational medicinal product, and/or a more likely alternative etiology exists.

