#### **4.10.6. Concomitant Medications**

Concomitant medications will be defined as those medications that were initiated after study drug administration or those that were ongoing at the time of study drug administration. If the start date or stop date of a medication is partially missing, the date will be compared as far as possible with the date of the start of administration of study drug. The medication will be assumed to be prior medication if it cannot be definitively shown that the medication did not start or continue during the treatment period. The following approach will be taken:

- If the start date of medication is complete and occurs on or after the day of administration of study treatment, the medication will be assumed concomitant. If the start date occurs prior to administration of study treatment but the end date is on or after the administration of study treatment date or the medication is recorded as ongoing, the medication will be considered concomitant.
- If the start day is missing but the start month and year are complete, a medication will only be excluded as being concomitant if the start month/year is before the month/year of study drug administration and if the stop date (either full date, month and year if missing day, or year if missing month and day) is before study drug administration.
- If the start day and month are missing but the start year is complete, a medication will only be excluded as concomitant if the start year is before the year of study drug administration and if the stop date (either full date, month and year if missing day, or year if missing month and day) is before study drug administration.
- If the start date is completely missing and the stop date is prior to administration of study treatment or completely missing, the medication will be assumed to be a prior medication.

All prior and concomitant medications (CM) will be presented in a data listing with flags indicating whether each medication was prior and/or concomitant. The listings will include type of medication (general concomitant or pain/restrictive) and whether the CM was used for treatment of an AE.

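### For AEs with an incomplete start date or time, three bullets in SAP 4.10.1 exclude on a pre-dose start alone, against the SAP's own rule that a worsened pre-existing event is treatment-emergent

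*SAP*

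**What the plan says.** SAP 4.10.1 treats two kinds of event as treatment-emergent: those that begin after study treatment, and "any event that was present at baseline but worsened in intensity through the end of the study". Protocol 9.4.4 likewise includes events that became more severe after dosing.

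The SAP then deals with incomplete starts. The scope is set by "If the start date/time of an AE is partially or completely missing", and the principle is worst case: "The AE will be assumed to be treatment emergent if it cannot be definitively shown that the AE did not occur or worsen" in the treatment-emergent period. Four bullets follow as the general rules to be used:

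- Bullet 1 (date known, time missing): "an AE will only be excluded as being treatment emergent if the start date is before the date of study drug administration or if" the event stopped before dosing.
- Bullet 2 (day missing): excluded only "if the start month/year is before the month/year of study drug administration or if the stop date/time is before study drug administration".
- Bullet 3 (day and month missing): the same, with the year in place of the month and year.
- Bullet 4 (start wholly missing): kept unless the event stopped before dosing.

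Later in 4.10.1, TEAEs are placed in reporting periods by date and time of onset. Every listed period opens at baseline, at the first dose or later.

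On data collection, Protocol 8.1.2 states: "Minimum information required for each AE includes type of event, duration (start and end dates), severity". Note 17 to Protocol Table 1 states: "AEs and Concomitant Medications will be captured from Day 1 (post injection"). Protocol 7.9.3, 7.9.5 and 8.1.5 have findings that worsen from baseline recorded as AEs.

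**The concern.** The definition and the worst-case sentence both cover worsening. Bullets 1 to 3 do not: a pre-dose start is enough for exclusion whatever happened afterwards. A programmer who codes the bullets as the operating rule gets a result that the definition forbids.

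The outcome is also inverted. An ongoing, worsened event with no start date at all is kept under bullet 4, while the same event with a known pre-dose year is dropped under bullet 3.

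Safety of repeat dosing is the primary objective. The patients have an already symptomatic index knee and may have controlled chronic conditions (Protocol 7.3.1), so worsening of something already present is a form of harm that the TEAE tables are meant to show. An event classed as not treatment-emergent is missing from the overall, severity, relatedness and index-knee TEAE summaries.

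**Working it through.** The plan gives no figure to reproduce here, so the check is logical: apply the bullets and the definition to the same cases and compare.

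**Inputs.** The TEAE definition, the worst-case sentence and bullets 1 to 4, all from SAP 4.10.1. For illustration, dosing is set at 15 March 2017, an assumed date. The event has not stopped before dosing. Seven start patterns, each with and without worsening after dosing, give 7 × 2 = 14 cases.

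**Rules compared.**
- Bullets: exclude if the known part of the start precedes dosing.
- Definition with worst-case sentence: exclude only if the known part of the start precedes dosing and the event did not worsen.

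| Known start | Precedes dosing? | Worsened: bullets / definition | Not worsened: bullets / definition |
|---|---|---|---|
| 1 March 2017, time missing | yes | exclude / count (**conflict**) | exclude / exclude |
| February 2017, day missing | yes | exclude / count (**conflict**) | exclude / exclude |
| 2016, day and month missing | yes | exclude / count (**conflict**) | exclude / exclude |
| 15 March 2017, time missing | not shown | count / count | count / count |
| March 2017, day missing | not shown | count / count | count / count |
| 2017, day and month missing | not shown | count / count | count / count |
| wholly missing | not shown | count / count | count / count |

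**Result.** There are three conflicts in 14 cases, one for each of bullets 1 to 3, and all are worsened events. This counts logical cases and says nothing about how often they occur.

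**Candidate repairs.**
- Adding a no-worsening condition to the pre-dose-start limb gives agreement in all 14 cases.
- Changing *or* to *and* does not work. The three worsened cases are then counted correctly, but the three pre-dose cases that never worsened are now counted too, against the definition.

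**Period assignment.** Suppose a worsened event is kept but still carries its pre-dose onset. Every listed period opens at baseline, at the first dose or later, so the event falls before all of them. Correcting the bullets alone would therefore not bring it into the period tables.

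**The case against.** The strongest reply is that the section already protects worsened events. The worst-case sentence governs the bullets, and a rule that an event is excluded only if a condition holds is, strictly, a necessary condition rather than an instruction to exclude. That reading is possible. But the bullets are presented as the rules to be used, and bullet 4 is plainly operative, so the text can be programmed either way. It needs correcting.

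The second reply is that nothing may be lost. AEs are captured after the Day 1 injection and a worsening is itself recorded as an AE, so its natural onset may be the date of worsening. This stands as a limit: an event is lost only if the original onset date is entered, and the documents leave that open.

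A reader might infer more than the documents support:

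- *That the SAP drops every event that began before dosing.* It does not. The bullets apply only to incomplete start dates or times, and exclude on the start only when the known part precedes dosing.
- *That bullet 1 catches most AEs because the protocol's minimum data list dates and not times.* That list is a minimum, and the SAP assigns periods by date and time of onset, so times may well be collected.
- *That all the incomplete-date rules bias counts downwards.* The contradiction does, where it bites. But the same bullets keep starts in the dosing month or year that may in truth precede dosing.
- *That the loss can be put as a percentage.* Scaling the 46.0% TEAE rate in Protocol 5.2.8 would need a share of affected patients that no document gives.
- *That the wording in SAP 4.10.6 proves a slip.* The medication rule, "a medication will only be excluded as being concomitant if the start month/year is before the month/year of study drug administration and if" the stop also precedes dosing, has no worsening limb and sits under the opposite default.

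**Conclusion.** The contradiction within SAP 4.10.1 is real. For AEs with an incomplete start whose known part precedes dosing, bullets 1 to 3 make that start sufficient for exclusion, while the definition and the worst-case sentence require a worsened event to be counted.

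The consequence is conditional. A worsened pre-existing condition could be left out of the TEAE summary tables if the bullets are coded literally and the event is entered under its original onset date. It would still be listed, because SAP 4.2.1 lists all collected data and SAP 4.10.1 lists deaths, SAEs and AEs leading to discontinuation for all patients. The number affected cannot be computed from the documents. The correction is worth making because it concerns the primary safety derivation and costs little.

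**What to change.** In bullets 1 to 3 of SAP 4.10.1, exclude an event only if:

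- (a) it stopped before the first study drug administration, or
- (b) the known part of its start precedes the first administration and it did not worsen in intensity afterwards.

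If worsening cannot be determined, keep the event as treatment-emergent, as the worst-case sentence already requires. Naming the first administration also settles which of the two doses the rule refers to.

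State as well that a worsened pre-existing condition takes the date of worsening as its TEAE onset when events are assigned to the reporting periods in 4.10.1.

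The cost is a wording change and a small change to the derivation. The documents do not show whether a date of worsening or a severity history is collected, so the sponsor should check this. Without that date, a retained event counts as treatment-emergent but cannot be placed in a period. The downside is that a few more events may count as treatment-emergent.
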